### **7.2.2.2. Dose Escalation Method**

In this study, dose escalation will be driven by safety using the 3+3 method. Dose escalation will proceed as follows:

Dose Level 1 (25 mg):

- 3 patients will be enrolled. If 1 out of 3 evaluable patients for DLT experience a DLT, 3 additional patients will be enrolled in the same dose level.
- If 0 out of 3, or 1 out of 6 evaluable patients for DLT experience a DLT, the dose will be escalated to Dose Level 2.
- If dose escalation is made based on 3 evaluable patients in Dose Level 1 and Dose Level 2 is judged as intolerable, an additional 3 patients will be enrolled in Dose Level 1 and tolerability of Dose Level 1 will be evaluated based on a total of 6 patients' data.

Dose Level 2 (50 mg):

- 6 patients will be enrolled. If  $\leq 1$  out of 6 evaluable patients for DLT experience a DLT, the dose will be judged as tolerable.

All dose levels:

- If 2 patients experience DLTs at any given dose, the sponsor will examine the safety data and consult with the SAC as needed. With the consultation, the sponsor and the primary investigator will decide if the dose is intolerable or additional patients will be enrolled to the same dose level.
- If  $\geq 3$  patients experience DLTs at any given dose, it will be judged that the dose is not tolerable for Japanese patients.

[figure not shown]
An evaluable patient for DLT is defined as a patient who takes  $\geq 75\%$  of the planned dose in Cycle 1 (first 28 days) or a patient who experiences DLT in Cycle 1 (first 28 days). A patient who takes  $<75\%$  in Cycle 1 due to reasons other than drug-related toxicity (for example, early discontinuation due to progressive disease) will be considered nonevaluable for DLT and replaced by a new patient. If a patient takes  $<75\%$  in Cycle 1 due to drug-related toxicities, the investigators and Lilly clinical research personnel will discuss whether the toxicities could be

deemed to be dose-limiting, and will consult with the SAC if needed. If it is not considered DLT, the patient is deemed to be nonevaluable for DLT and will be replaced by a new patient.

The reason for taking <75% of the planned dose needs to be documented appropriately and may be confirmed by the sponsor.

Dose escalation decisions will be made by agreement between the primary investigator and the sponsor, with a consultation with the SAC as needed. Additional patients may be enrolled at a specific dose level to characterize PK/PD or safety profile.

Figure JJCC.2 illustrates the dose level transition method and tolerability confirmation.

Abbreviations: DLT = dose-limiting toxicity; SAC = Safety Assessment Committee.

**Figure JJCC.2. Schema of dose level transition.**

### 7.2.3. Dose Adjustments and Delays

#### 7.2.3.1. Dose Adjustments within Cycle 1

If a patient experiences a DLT, the patient should be discontinued from study treatment, unless, in the opinion of the investigator, the patient can clinically benefit from continuation of LY3039478 at a reduced dose level after the toxicity has recovered to baseline or Grade 1. For patients receiving Dose Level 1 (25 mg TIW), study treatment at 25 mg can be resumed and the dosing schedule may be modified, while safety assessment will be maintained as described in the Study Schedule (Attachment 1). For these situations, agreement between the investigator and the sponsor is required and the patient will re-sign the ICF for the continuation of study treatment.

If a patient experiences a toxicity which does not meet the criteria for a DLT, but requires dose omission in the opinion of investigator, the dose can be omitted. Dosing may resume at the same dose after the toxicity resolves to baseline or Grade 1; however, the dose(s) omitted for tolerability during a cycle will not be replaced.

#### 7.2.3.2. Dose Adjustments within Cycle 2 and Beyond

If a patient treated at a given dose level experiences a DLET, the treatment will be discontinued for that patient. The dose may be resumed at a reduced dose level after the toxicity resolves to

baseline or Grade 1 if the investigator determines that it is in the best interest of the patient. For patients receiving 25 mg, the dosing schedule for resuming study treatment can be modified, while safety assessment will be maintained as described in the Study Schedule ([Attachment 1](#)). For these situations, agreement between the investigator and the sponsor is required and the patient will re-sign the ICF for the continuation of study treatment.

If a patient experiences a toxicity which does not meet the criteria for a DLET, but requires dose omission in the opinion of the investigator, the dose can be omitted. Dosing may resume at the same dose level after the toxicity resolves to baseline or Grade 1; however, the dose(s) omitted for tolerability during a cycle will not be replaced. A DLET is defined as an AE occurring in any cycle (other than Cycle 1) that would have met the criteria for DLT if it had occurred during Cycle 1.

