#### **7.2.2.1. Dose-Limiting Toxicity Determination**

Dose-limiting toxicity is defined as an AE during Cycle 1 (first 28 days) that is related to study drug and fulfills any one of the following criteria using the National Cancer Institute (NCI) Common Terminology Criteria for Adverse Events (CTCAE) v 4.0:

- CTCAE Grade  $\geq 3$  non-hematological toxicity. Exceptions will be made for:
  - nausea, vomiting, or constipation that lasts  $<72$  hours and that can be controlled with treatment
  - asymptomatic electrolyte disturbance that can be controlled with treatment
  - Grade 3 diarrhea, stomatitis, or mucositis that lasts  $\leq 5$  days and that can be controlled with standard treatment
  - transient ( $<7$  days) Grade 3 elevations of ALT and/or AST, that are not accompanied by a Grade 2 bilirubin increase, unless there is a clear alternative cause (for example, worsening biliary obstruction) if agreed by the study investigator and Lilly CRP/CRS
  - tumor lysis/necrosis syndrome
- CTCAE Grade 4 hematological toxicity of  $>5$  days duration
- CTCAE Grade  $\geq 3$  anemia which requires a transfusion of packed red blood cells
- Any febrile neutropenia
- Neutropenia that requires treatment with granulocyte-colony stimulating factors (G-CSFs). However, the investigators and Lilly clinical research personnel will comprehensively determine the dose-limiting toxicity based on the clinical course of the patient, including laboratory test results.

- CTCAE Grade 3 thrombocytopenia with bleeding, Grade 3 thrombocytopenia which requires platelet transfusion, or Grade 4 thrombocytopenia
- Any other significant toxicity deemed by the investigators and Lilly clinical research personnel to be dose-limiting (for example, any toxicity that is possibly related to the study medication that requires the withdrawal of the patient from the study during Cycle 1)

Dose-limiting toxicity will be confirmed based on the agreement between the primary investigator and the sponsor, with a consultation with the Safety Assessment Committee (SAC) as needed.

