#### **7.2.3.3. Dose Adjustments Between Cycles**

Before the start of each cycle, hematological and nonhematological toxicities (except alopecia and fatigue) must resolve to baseline or Grade 1. The start of a cycle may be delayed up to 3 weeks to allow sufficient time for recovery. Patients not recovering from toxicity to baseline or Grade 1 within 3 weeks after development should be discontinued from study treatment.

The dose for a patient in Dose Level 2 should be reduced for all subsequent cycles of therapy to Dose Level 1 in the cases below:

1. if the investigator determines that it is in the best interest of the patient, or
2. if the patient experiences dose omission of >7 doses in a single cycle due to toxicities which are not considered DLTs/DLETs.

If a patient requires omission of >3 doses for tolerability at the reduced dose level in a single cycle, the patient should be discontinued from study treatment.

Study treatment should be discontinued for patients started at 25 mg TIW who experience a toxicity requiring dose reduction. For such patients who experience toxicities that may cause discontinuation from study treatment as noted above, the dosing may be resumed at a reduced dose level after the toxicities have recovered to baseline or Grade 1 if, in the opinion of the investigator, those patients can clinically benefit from continuation of study drug. For patients at 25 mg, the dosing schedule for resuming study treatment can be modified while safety assessment will be maintained as described in the Study Schedule ([Attachment 1](#)). For the exceptions noted above, agreement between the investigator and the sponsor are required and the patient will re-sign the ICF for the continuation of study treatment.

For patients requiring a dose reduction, re-escalation to the original dose level is not permitted.

A delay in the start of a cycle due to holidays, weekends, bad weather, or other unforeseen circumstances will be permitted up to 3 working days.

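### A related event that meets the DLT criteria but starts while Cycle 2 is delayed is neither a DLT nor a DLET; if it recovers in time, a 50 mg patient may restart at 50 mg, and the DLET summary omits it

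*Protocol*

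**What the plan says.** Protocol 7.2.2.1: "Dose-limiting toxicity is defined as an AE during Cycle 1 (first 28 days) that is related to study drug" and that meets a listed criterion. One criterion is "Grade 3 thrombocytopenia which requires platelet transfusion, or Grade 4 thrombocytopenia". The catch-all criterion for other significant toxicity falls under the same 28-day limit.

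Protocol 7.2.3.2: "A DLET is defined as an AE occurring in any cycle (other than Cycle 1) that would have met the criteria for DLT" had it occurred during Cycle 1.

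The dosing rules are in three places:

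- **DLT (7.2.3.1):** "If a patient experiences a DLT, the patient should be discontinued from study treatment, unless, in the opinion of the investigator", the patient can benefit from a reduced dose after recovery. Sponsor agreement and renewed consent are needed.
- **DLET (7.2.3.2):** "If a patient treated at a given dose level experiences a DLET, the treatment will be discontinued for that patient". Dosing may resume at a reduced level after recovery if the investigator judges that best for the patient. For this, "agreement between the investigator and the sponsor is required and the patient will re-sign the ICF for the continuation of study treatment".
- **Between cycles (7.2.3.3):** toxicity, except alopecia and fatigue, must first return to baseline or Grade 1. "The start of a cycle may be delayed up to 3 weeks to allow sufficient time for recovery". A 50 mg patient goes down to 25 mg "if the investigator determines that it is in the best interest of the patient, or" after more than 7 doses omitted in one cycle for toxicities that are not DLTs or DLETs.

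Protocol 7.2.1 sets the cycle at 28 days. SAP 6.1 makes Day 1 of a cycle the date of its first dose. SAP 6.11.2 summarizes DLETs in the safety analysis set but does not define the term.

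**The concern.** The DLET exists to carry the DLT criteria past the DLT window. As worded, the two definitions meet only if Cycle 2 starts on time. If it starts late, there is an interval after the DLT window has closed and before any cycle other than Cycle 1 has begun.

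Two things depend on the classification. One is the dosing rule for a 50 mg patient: a DLT or DLET forces a reduction if treatment resumes and brings in the sponsor and a new consent, whereas the between-cycle rule leaves the dose to the investigator. The other is the DLET summary, the only SAP output that applies the DLT criteria after Day 28.

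**Working it through.** The plan gives no figure to reproduce. The check is to classify each onset date.

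**Inputs.** DLT window: Days 1 to 28 (7.2.2.1). DLET window: any cycle other than Cycle 1 (7.2.3.2). Cycle length: 28 days (7.2.1). Longest delay for toxicity: 3 weeks, or 21 days (7.2.3.3). Start of Cycle 2: date of its first dose (SAP 6.1).

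**Count.** With a delay of D days, the first Cycle 2 dose is on Day 29+D. Onset by Day 28 can be a DLT, and onset on or after Day 29+D can be a DLET. Uncovered dates = (28+D) − 29 + 1 = D.

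| Delay D | First Cycle 2 dose | Uncovered onset dates | Number |
|---|---|---|---|
| 0 | Day 29 | none | 0 |
| 3 | Day 32 | Days 29–31 | 3 |
| 7 | Day 36 | Days 29–35 | 7 |
| 14 | Day 43 | Days 29–42 | 14 |
| 21 | Day 50 | Days 29–49 | 21 |

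**Two readings of a cycle.** If a cycle is 28 days, the delay days belong to no cycle. Under the SAP's Cycle Day rule they are Cycle 1, Day 29 or later: past the DLT window, yet still in the one cycle that the DLET definition excludes. The count is the same.

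**The edges.** An event on the date of the first Cycle 2 dose is Cycle 2 Day 1 under the SAP's date rule, so it can be a DLET. Day 29 is arguable, because Attachment 1 lists the tests for Day 1 of the next cycle under Cycle 2. If Day 29 is read as a Cycle 2 visit, the count for a delayed start is D − 1.

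**What still forces a stop.** Section 6.3.2 requires discontinuation for Grade 4 nonhematological toxicity and for toxicity not back to baseline or Grade 1 within 3 weeks, whatever the cycle. Section 7.2.3.3 repeats the second. What remains is every other qualifying event that recovers in time, for example Grade 4 thrombocytopenia or a qualifying Grade 3 nonhematological event.

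**Example at 50 mg.** Cycle 2 is held on Day 29 for a toxicity that is not a DLT and that resolves in time. No more than 7 doses were omitted in Cycle 1. Related Grade 4 thrombocytopenia starts on Day 33 and is Grade 1 by Day 42, which is 42 − 33 = 9 days and within the 21 allowed. Cycle 2 starts on Day 43 (D = 43 − 29 = 14). Compare three onset dates for this event:

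| Onset | Class | If treatment resumes |
|---|---|---|
| Day 28 | DLT | Reduced dose, with sponsor agreement and renewed consent |
| Day 33, in the delay | Neither | 50 mg permitted; reduction at the investigator's discretion |
| Day 43, Cycle 2 Day 1 | DLET | Reduced dose, with sponsor agreement and renewed consent |

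**After the fix.** If a DLET is any qualifying event with onset after Day 28, the number of uncovered dates is 0 for every delay in the first table.

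**The case against.** **The intent is plain.** The DLET clause asks what would have counted had it happened in Cycle 1, so a sensible investigator would treat an event in the delay as a DLET. That may well happen, but the text does not require it. The SAP has no DLET definition of its own to direct the programmer.

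**The setting is narrow.** It needs a delayed Cycle 2 and a new event of DLT grade while off drug. Day 33 is 7 days after the scheduled Day 26 dose. At the mean half-life of 5 to 7 hours in protocol 5.3.4.2, those 168 hours are 168/7 = 24 to 168/5 ≈ 34 half-lives. This stands as a reason to expect few such events. However, the type of event is not remote: protocol 5.3.4.1 reports Grade 4 thrombocytopenia in 3 of the 5 patients with DLTs in Part A of the first-in-human study. The documents give no rate for onset during a delay.

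**The stop is not absolute on either side.** A reader might infer that a DLT or DLET ends treatment outright, and that an event in the delay escapes every stopping rule. Neither is right. After a DLT or DLET the investigator may favor resumption. During the delay, the two fixed triggers in 6.3.2 still apply, recovery before dosing is compulsory, and the investigator may stop or reduce. The difference is the forced reduction, the sponsor's agreement and the renewed consent.

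**Onset is an assumption.** The protocol speaks of an event during, or occurring in, a cycle, not of its onset. Fatigue is exempt from the between-cycle recovery rule, so qualifying Grade 3 fatigue that starts in the delay and persists could be read as occurring in Cycle 2. That exception stands.

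**Conclusion.** The gap is real under both readings of a cycle, and no other section closes it. Its size is D onset dates, up to 21 (D − 1 if Day 29 is given to Cycle 2), and 0 if Cycle 2 starts on time. It assumes that events are classified by date of onset.

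The consequences are limited to two. A 50 mg patient with a qualifying event outside the fixed triggers, who recovers in time, may restart at 50 mg without the safeguards that apply to the same event just before or after the delay. The descriptive DLET summary also omits the event.

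A reader might go further and infer that the escalation or tolerability decision is compromised, or that the event goes unreported. The documents do not support this. Those decisions rest on DLTs in the first 28 days, and the event remains in the AE listing and the TEAE tables. Nor can one missed event be stated as 1 of 6 patients: the DLET summary uses the safety analysis set, which can include replaced and additional patients. No probability is claimed. The point is minor.

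**What to change.** In protocol 7.2.3.2 and SAP 6.11.2, define a DLET as an AE with onset after Day 28 of Cycle 1, including during between-cycle delays, that would have met the DLT criteria had it occurred in Cycle 1. In 7.2.3.3, state that such an event during a delay is handled under 7.2.3.2.

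The cost is one sentence in each of the two protocol sections and one in the SAP, with no new data. The DLET count may be slightly higher, and a 50 mg patient with such an event can no longer resume at 50 mg. This wording also takes in qualifying events during the 30-day follow-up; if those are kept, tabulate them apart from events within a cycle. If the protocol can no longer be amended, the SAP sentence alone repairs the summary but not the dosing rule.

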#### **7.2.3.3. Dose Adjustments Between Cycles**

Before the start of each cycle, hematological and nonhematological toxicities (except alopecia and fatigue) must resolve to baseline or Grade 1. The start of a cycle may be delayed up to 3 weeks to allow sufficient time for recovery. Patients not recovering from toxicity to baseline or Grade 1 within 3 weeks after development should be discontinued from study treatment.

The dose for a patient in Dose Level 2 should be reduced for all subsequent cycles of therapy to Dose Level 1 in the cases below:

1. if the investigator determines that it is in the best interest of the patient, or
2. if the patient experiences dose omission of >7 doses in a single cycle due to toxicities which are not considered DLTs/DLETs.

If a patient requires omission of >3 doses for tolerability at the reduced dose level in a single cycle, the patient should be discontinued from study treatment.

Study treatment should be discontinued for patients started at 25 mg TIW who experience a toxicity requiring dose reduction. For such patients who experience toxicities that may cause discontinuation from study treatment as noted above, the dosing may be resumed at a reduced dose level after the toxicities have recovered to baseline or Grade 1 if, in the opinion of the investigator, those patients can clinically benefit from continuation of study drug. For patients at 25 mg, the dosing schedule for resuming study treatment can be modified while safety assessment will be maintained as described in the Study Schedule ([Attachment 1](#)). For the exceptions noted above, agreement between the investigator and the sponsor are required and the patient will re-sign the ICF for the continuation of study treatment.

For patients requiring a dose reduction, re-escalation to the original dose level is not permitted.

A delay in the start of a cycle due to holidays, weekends, bad weather, or other unforeseen circumstances will be permitted up to 3 working days.

### **7.3. Method of Assignment to Treatment**

Patients who meet all criteria for enrollment will be assigned to receive LY3039478 in this study. Before each patient's enrollment into the study, an eligibility check must be conducted between

the investigational site and the Lilly clinical research personnel to confirm that each patient meets all enrollment criteria. Upon confirmation of eligibility, the sponsor will confirm the dose, identification number assignment, and cohort for each patient. No dose escalations (that is, to the next cohort) can occur without prior discussion and agreement with the responsible Lilly CRP/CRS.

If investigators have eligible patients who have consented concurrently, >3 patients may be entered at a particular dose level provided that accrual has not ceased due to excessive toxicity. This enrollment procedure is allowed because of the advanced disease state of this patient population and the screening involved in defining eligibility. This event should be approved by the sponsor following discussions with the investigators.

#### **7.4. Blinding**

This is an open-label study.

#### **7.5. Concomitant Therapy**

No other chemotherapy, radiotherapy, immunotherapy, cancer-related hormone therapy, or experimental drugs will be permitted while patients are on this study. An exception will be made for prostate or breast cancer patients continuing gonadotropin-releasing hormone or luteinizing hormone-releasing hormone agonist therapy. The need for any form of radiotherapy (except palliative) will be cause for early discontinuation from the study. In addition, any disease progression requiring other forms of specific antitumor therapy will also necessitate early discontinuation from the study. Appropriate documentation for all forms of premedications, supportive care, and concomitant medications must be captured on the CRF.

Patients should receive full supportive care, with the exception that the routine use of granulocyte-colony stimulating factors (G-CSFs) is not permitted during this study. Patients should not receive G-CSFs prophylactically in any cycle. Granulocyte-colony stimulating factors may only be used for patients who have ANC<0.5 × 10^9/L, neutropenic fever, or documented infections while neutropenic and must be discontinued at least 24 hours before the start of the next cycle of treatment. Should the use of hematopoietic colony-stimulating factors (CSFs) be necessary, follow the American Society of Clinical Oncology (ASCO) recommendations for the use of CSFs (Smith et al. 2006). If clinically indicated at any time during the study, transfusions may be used according to ASCO guidelines (Schiffer et al. 2001; Rizzo et al. 2008).

Diarrhea should be managed by standard treatments as per institutional guidelines. Guidance for diarrhea standard management is provided in [Attachment 8](#).

All concomitant medications should be recorded throughout the patient's participation in the study.

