### ***6.3.2. Discontinuation of Patients from Study or Study Drug***

Patients who are discontinued from the study drug will have follow-up procedures performed as shown in the Study Schedule ([Attachment 1](#)).

Patients will be discontinued from the study drug in the following circumstances:

- Enrollment in any other clinical trial involving an investigational product or enrollment in any other type of medical research judged not to be scientifically or medically compatible with this study.
- Investigator/Physician Decision
  - the investigator/physician decides that the patient should be withdrawn from the study or study drug(s).
  - the patient, for any reason, requires treatment with another therapeutic agent that has been demonstrated to be effective for treatment of the study indication, discontinuation from the study drug(s) occurs prior to introduction of the other agent.
- Patient Decision
  - the patient requests to be discontinued from the study or study drug.
- Sponsor Decision

- Lilly stops the study or stops the patient's participation in the study for medical, safety, regulatory, or other reasons consistent with applicable laws, regulations, and GCP.
- The patient becomes pregnant.
- The patient has evidence of progressive disease by radiological assessments (RECIST v1.1). However, the patient may continue the study drug if, in the opinion of the investigator, the patient will clinically benefit from continuation of study drug, following discussion and approval by the sponsor. The patient will re-sign the informed consent form (ICF) for the continuation of study treatment.
- The patient has evidence of deteriorating clinical symptoms of progressive disease.
- The patient experiences unacceptable toxicity including, but not limited to, a Grade 4 nonhematological toxicity or a toxicity that does not resolve to baseline or Grade 1 within 3 weeks.
- The patient, treated at 25 mg TIW, experiences a toxicity requiring dose reduction. However, the patient may continue after the toxicity has recovered to baseline or Grade 1 if, in the opinion of the investigator, the patient will clinically benefit from continuation of study drug. The dosing schedule for resuming study treatment at 25 mg can be modified after agreement with the sponsor, while safety assessment will be maintained as [Attachment 1](#). The patient will re-sign the ICF for the continuation of study treatment.

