## 6.3. Handling of Dropouts or Missing Data

Missing data, except for dates, will not be imputed. They will be kept as missing in the data analyses, except for dates when used in calculations of relative study day, for which sponsor reporting standards will be utilized for imputation rules, defined as:

- The birth date will be imputed by assigning month and day with July 1st to calculate age.
- For the missing date of relative study day, the following imputation methods will be used:
  - If only the day of the month is unknown, the 15th of the month will be used.
  - If both the day and the month are unknown, July 1st will be used.
- When expanding the concomitant therapy, and previous therapy records across visits, the following imputation methods will be used:
  - For start date,
    - If the day component is unknown, then the 1st of the month will be used.
    - If the month are unknown, then January will be used.
    - If both the day and the month are unknown, January 1st will be used.
    - If the day, the month and the year are unknown, the date will be missing.
  - For end date,
    - If the day component is unknown, then the 30th of the month will be used.
    - If the month are unknown, then December will be used.
    - If both the day and the month are unknown, December 30th will be used.
    - If the day, the month and the year are unknown, the date will be missing.

Partial dates should be reported in all listings and not the imputed date.

Analyses of response will include all patients with measurable disease. Analyses of change in tumor size will include only patients with measurable disease and evaluable target lesion measures at baseline and at least one post-treatment visit.

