### 6.10.1. Efficacy Definitions

The following definitions for efficacy endpoints will be used:

**Overall response rate (ORR)** is the proportion of efficacy patients who achieved a complete response (CR) or partial response (PR) out of all efficacy patients. Depending on the histology, tumor responses will be measured and recorded using the appropriate guidelines [RECIST 1.1 (Eisenhauer et al. 2009), the Response Assessment in Neuro-Oncology criteria for glioblastoma (Wen et al. 2010)]. To confirm objective responses, all lesions should be radiologically assessed, and the same radiologic method used for the initial response determination should be repeated at least 4 weeks following the initial observation of an objective response, using the same method that was used at baseline. For patients who discontinue study treatment without objectively measured progressive disease, the radiological tumor assessment is not required.

**Best response** is determined from a sequence of responses assessed. Two objective status determinations of CR before progression are required for a best response of CR. Two determinations of PR or better before progression, but not qualifying for a CR, are required for a best response of PR.

**Change in tumor size** will be assessed in each patient with measurable disease using radiographic imaging. Tumor size is the sum of the tumor measurements for target lesions at each tumor evaluation. Change in tumor size is defined as the percent change in tumor size from the baseline evaluation to the minimum post-dose evaluation. Other definitions of change in tumor size may be explored (including specific time points, and AUC formulations).

**Duration of Response** will be calculated for ORR and is defined only for responders. It is measured from the date of first evidence of a confirmed response to the date of first progression of disease or the date of death due to any cause, whichever is earlier. For each patient who is not known to have died or to have had a progression of disease as of the data-inclusion cut-off date, duration of response will be censored at the date of last objective response assessment prior to the date of any subsequent systemic anticancer therapy.

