**Duration of Stable Disease** will be calculated only for patients with best response of stable disease. It is measured from the date of start of treatment to the date of first progression of disease or the date of death due to any cause, whichever is earlier. For each patient who is not known to have died or to have had a progression of disease as of the data-inclusion cut-off date, duration of stable disease will be censored at the date of last objective response assessment prior to the date of any subsequent systemic anticancer therapy.

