### **6.10.2. Efficacy Analyses**

Tumor markers and disease progression data will be listed.

Reported lesion data (target/ non-target or measurable/ nonmeasurable) and investigator assessment of response will be listed.

The following efficacy endpoints, detailed in Section 6.10.1 will be summarized as appropriate:

- Overall response rate
- Best overall response
- Change in tumor size. A waterfall plot of change in tumor size will be produced. All patients with at least one target lesion measurement will be represented in the plot.
- PET parameters will be listed. Change in SUVmax will be presented using a waterfall plot for patients with evaluable baseline and post-treatment PET imaging data, if data warrant.
- Duration of response
- Duration of stable disease

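### Target-lesion irradiation on study is not a stop for change in tumor size or for the two duration endpoints, although palliative radiotherapy does not trigger discontinuation

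*Protocol*

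**What the plan says.** Protocol 7.5 (Concomitant Therapy) begins with a general ban on other anticancer treatment during the study, radiotherapy included. The only exception attached to that ban is for certain hormone agonists in breast and prostate cancer. Two sentences later it says: "The need for any form of radiotherapy (except palliative) will be cause for early discontinuation from the study". Nothing states which lesions may be irradiated.

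SAP 6.10.1 defines tumor size as the sum over target lesions. It then states: "Change in tumor size is defined as the percent change in tumor size from the baseline evaluation to the minimum post-dose evaluation". No therapy or date ends the period over which that minimum is taken. SAP 6.10.2 adds: "A waterfall plot of change in tumor size will be produced".

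For patients without known progression or death at the cut-off date, SAP 6.10.1 says that "duration of response will be censored at the date of last objective response assessment prior to the date of any subsequent systemic anticancer therapy", and likewise that "duration of stable disease will be censored at the date of last objective response assessment prior to the date of any subsequent systemic anticancer therapy". In all other patients both durations run to progression or death.

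**The concern.** Documenting antitumor activity is a secondary objective, and the study has one arm, so no control separates a radiation effect from a drug effect. If a target lesion is irradiated for palliation and the patient stays on treatment, taking the minimum post-dose sum tends to select the scan on which radiation has worked best. The durations also keep counting after irradiation, because local radiotherapy is not systemic therapy. Followed as written, the SAP would show both as activity under LY3039478.

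**Working it through.** **The plan's own figure.** The planned 9 to 12 patients follow from the cohort sizes: 3 + 6 = 9 and 6 + 6 = 12. One affected patient is 1/12 = 8.3% to 1/9 = 11.1% of the study, or 1/6 = 16.7% of a six-patient dose level. The point does not depend on this figure; it shows how much one patient weighs.

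**Step 1: can an irradiated patient remain on study?** Several rules narrow the group.
- Protocol 7.5: "any disease progression requiring other forms of specific antitumor therapy will also necessitate early discontinuation from the study".
- Protocol 6.3.2 stops study drug for radiological progression, and separately for worsening symptoms of progression.
- Protocol 6.3.2 also stops it when "the patient, for any reason, requires treatment with another therapeutic agent that has been demonstrated to be effective for treatment of the study indication". Whether palliative radiotherapy is such an agent is arguable.

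What remains is a patient whose target lesion needs palliation without radiological progression and without deterioration attributed to progression, or one kept on drug under the exceptions that 6.3.2 allows. That group is small but not empty.

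**Step 2: does another rule remove the post-irradiation assessments?**
- SAP 6.3: "Analyses of change in tumor size will include only patients with measurable disease and evaluable target lesion measures at baseline", and at one or more later visits. Neither document says that irradiation makes a lesion non-evaluable.
- Attachment 9 calls target lesions not evaluable only when the scan is incomplete or the measurement method has changed.
- Attachment 9's rule on irradiated lesions decides measurability at baseline.
- Attachment 9 ends the period for best overall response at new anticancer therapy, but only for that endpoint.

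None of these acts on change in tumor size or on the durations.

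**Step 3: size for change in tumor size.** The documents give neither the frequency of palliative radiotherapy nor the shrinkage it causes, so these values are assumed. One of k equal target lesions shrinks from 30 to 10 mm, a fraction f = 20/30 = 66.7%, and the others do not change. The change in the sum is -f/k:
- k = 1: -67%
- k = 2: -33%
- k = 3: -22%
- k = 5: -13%

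More generally, if the irradiated lesion is a share w of the baseline sum and shrinks by s, the bar is -w × s. With w = 0.50 and s = 60% it is -30%.

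**Step 4: size for the durations.** Scan days come from Attachment 1, assuming no cycle delays.
- End of Cycle 2: Cycle 3 Day 1 is 2 × 28 + 1 = 57, and the window opens 10 days earlier, so day 47 to 57.
- Cycle 4 Day 15: 3 × 28 + 15 = 99.
- Cycle 6 Day 15: 5 × 28 + 15 = 155.
- Cycle 8 Day 15: 7 × 28 + 15 = 211.

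Stable disease, irradiation just after the Cycle 2 scan, no progression seen:
- By Cycle 4 Day 15: 99 - 57 = 42 to 99 - 47 = 52 days added. With the 3-day window on the later scan: 96 - 57 = 39 to 102 - 47 = 55.
- By Cycle 6 Day 15: 155 - 57 = 98 to 155 - 47 = 108 days. With the window: 152 - 57 = 95 to 158 - 47 = 111.

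Response, confirmed at day 99 and irradiated after that: 155 - 99 = 56 days added at Cycle 6 Day 15, and 211 - 99 = 112 by Cycle 8 Day 15.

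These are not upper limits. Treatment has no fixed end, and each further scan adds 2 × 28 = 56 days.

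**Step 5: patients who later progress or die.** The censoring sentences do not reach them. Take a patient who is stable at day 57, irradiated next, and progresses on the day-155 scan. Stable disease is recorded with an event at day 155. Replacing the word for systemic therapy with a broader one leaves that at day 155, because the sentence applies only when no progression or death is known. Only a rule that applies whatever follows would censor at day 57, which is 155 - 57 = 98 days earlier.

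**The case against.** The strongest reply starts with the opening ban in 7.5. Read alone, it forbids palliative radiotherapy, and the later sentence says only that palliative need does not cause discontinuation. A reader might infer that 7.5 plainly permits irradiation of any lesion; the section is not that clear. The gap survives either reading. If the ban governs, such irradiation is a deviation that does not remove the patient from study, and the SAP still has no rule for the later scans.

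Second, the event is remote. Palliative radiotherapy is usually given for tumor symptoms, and worsening symptoms of progression already stop treatment. The duration-of-response example also needs a lesion to require palliation in a patient with a confirmed response. This stands, and it limits the weight of the point.

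Third, one irradiated patient among 9 to 12 could be recognized and footnoted. Lesion data are listed per patient, supportive care is captured on the CRF, and SAP 6.10.1 leaves room for other definitions of change in tumor size. This stands in part. SAP 6.9 names outputs for prior radiotherapy and for post-treatment therapies, but none for radiotherapy given during treatment.

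Fourth, a tempting remedy is to allow palliative radiotherapy to non-target lesions only. That would make a stable patient with a painful target lesion forgo palliation or leave the study. The objection is right, and that restriction should not be adopted.

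**Conclusion.** The point holds as a minor gap. A patient can stay on study after a target lesion is irradiated. No rule then stops change in tumor size, and the duration rules stop only for systemic therapy in patients without known progression or death. The sizes in the working rest on assumed shrinkage and an assumed irradiation date, so they illustrate the mechanism and do not forecast a bias.

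Three stronger readings go beyond the documents:
- A reader might infer that best overall response is affected in the same way. Attachment 9 already ends it at new anticancer therapy; only whether palliative radiotherapy counts is unclear.
- A reader might take the added days as caused by radiation. They are time after irradiation that counts toward the endpoint. A new lesion or non-target progression would still end both durations.
- A reader might fear for the tolerability conclusion. Escalation rests on safety, with PK as support, and no dose decision uses response. Efficacy is descriptive and no hypothesis is tested.

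**What to change.** 1. In SAP 6.10.1, exclude target-lesion assessments made after on-study irradiation of a target lesion from change in tumor size and the waterfall plot. A patient irradiated before the first on-treatment scan then has no usable bar and should be listed as such.
2. In both duration definitions, state that a patient who receives any subsequent anticancer therapy, including radiotherapy to a target lesion, before progression or death is censored at the last objective assessment before that therapy, whether or not progression or death follows.
3. In Protocol 7.5, reconcile the opening ban with the palliative exception. Do not limit palliation to non-target lesions.

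The cost is one added sentence and two revised definitions in SAP 6.10.1, and a clarifying phrase in 7.5. An affected patient loses later assessments, which could include genuine drug-related stability. The date and site of on-study radiotherapy must be recorded and linked to the lesion, and a listing of it should be added to SAP 6.9.
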